8.5.2. Method of Detecting AEs and SAEs

Care will be taken not to introduce bias when detecting AEs and/or SAEs. Open-ended and nonleading verbal questioning of the subject is the preferred method to inquire about AE occurrences.

8.5.3. Follow-up of AEs and SAEs

After the initial AE/SAE report, the investigator is required to proactively follow each subject at subsequent visits/contacts. All SAEs will be followed until resolution, stabilization, the event is otherwise explained, or the subject is lost to follow-up (see Section [7.3](#)). Further information on follow-up procedures is provided in Appendix 2 (see Section [10.2](#)).

8.5.4. Regulatory Reporting Requirements for SAEs

- Prompt notification – within 24 hours of SAE awareness - by the investigator to the sponsor of an SAE is essential so that legal obligations and ethical responsibilities towards the safety of subjects and the safety of the IMP under clinical investigation are met.
- The sponsor has a legal responsibility to notify both the local regulatory authority and other regulatory agencies about the safety of the IMP under clinical investigation. The sponsor will comply with country-specific regulatory requirements relating to safety reporting to the regulatory authority, institutional review board (IRB)s/ independent ethics committee (IEC)s, and investigators.
- An investigator who receives an investigator safety report describing an SAE or other specific safety information (e.g., summary or listing of SAEs) from the sponsor will review and then file it in the investigator site file and will notify the IRB/IEC, if appropriate according to local requirements.

8.5.5. Pregnancy

- Details of all pregnancies in female subjects and female partners of male subjects will be collected after the start of IMP and until the end of trial visit.
- If a pregnancy is reported, the investigator will record pregnancy information on the appropriate form and submit it to the sponsor within 24 hours of learning of the female subject or female partner of male subject (after obtaining the necessary signed informed consent from the female partner) pregnancy.
- While pregnancy itself is not considered to be an AE or SAE, any pregnancy complication or elective termination of a pregnancy for medical reasons will be reported as an AE or SAE.
- Abnormal pregnancy outcomes (e.g., spontaneous abortion, fetal death, stillbirth, congenital anomalies, ectopic pregnancy) are considered SAEs and will be reported as such.
- The subject/pregnant female partner will be followed to determine the outcome of the pregnancy. The investigator will collect follow-up information on the subject/pregnant female partner and the neonate, and the information will be forwarded to the sponsor.
- Any posttrial pregnancy-related SAE considered reasonably related to the IMP by the investigator will be reported to the sponsor (see Section [8.5.4](#)). While the investigator is not obligated to actively seek this information in former trial subjects/pregnant female partner, he or she may learn of an SAE through spontaneous reporting.

8.6. Pharmacokinetics

- PK data will be collected at a pre-selected number of trial sites in a subgroup of approximately 10 subjects.
- Blood samples of approximately 3 mL will be collected for measurement of plasma concentrations of C21 as specified in the SoA (see Section 1.3). At Day 1 (Visit 2), blood samples will be collected before the first IMP administration and 30 minutes, 1, 2, 3, 4 and 6 hours after the IMP administration.
- Instructions for the collection and handling of biological samples will be provided by the sponsor. The actual date and time (24-hour clock time) of each sample as well as the date and time of the IMP administration will be recorded.
- PK data will not be reported to the trial sites, sponsor or blinded CRO/vendor staff until the trial has been unblinded.
- The individual plasma concentration data, and the actual time for IMP administration and blood sampling will be used throughout the analyses.
- All C21 plasma concentration data collected in this trial can be included in population PK and population PK/PD analyses with the objective of exploring the impact of covariates (e.g., body weight and age) on the PK of C21, or the relationship between the C21 exposure and selected efficacy and safety endpoints. Any population PK and population PK/PD analyses will be reported separately.
- From the plasma C21 concentration data analysis, the following PK variables will be derived using non-compartmental analysis:
 - C_{\max} - Observed maximum plasma concentration of C21.
 - t_{\max} - Time to reach C_{\max} following IMP administration.
 - $AUC_{(0-6)}$ - Area under the plasma concentration curve from time zero to 6 hours.
 - AUC_{last} - Area under the plasma concentration-time curve from time zero to the last quantifiable concentration.
 - $AUC_{(0-\infty)}$ - Area under the plasma concentration-time curve from time zero extrapolated to infinity.
 - $t_{1/2}$ - Apparent terminal half-life.
 - C_6 - Actual plasma concentration of C21 at 6 hours after IMP administration.

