1.1. Synopsis

Protocol Title: A randomized, double-blind, placebo-controlled, parallel group, phase 3, multicenter trial investigating the efficacy and safety of C21 as add on to standard of care in adult subjects with COVID-19.

Brief Title: A trial to investigate recovery from COVID-19 with C21 in adult subjects.

Rationale: The corona virus disease 2019 (COVID-19) is an ongoing pandemic caused by severe acute respiratory syndrome corona virus 2 (SARS-CoV-2). Although several therapeutic agents have been evaluated for the treatment of COVID-19, the morbidity and mortality are still significant. The need for safe, effective, and convenient COVID-19 drugs is likely to remain even after the launch of vaccine programs. The safety and efficacy of C21 in subjects with COVID-19 have been investigated in a phase 2 trial. The results show that C21, as add on to standard of care (SoC), reduced the need for extended oxygen supplementation and had a favorable benefit/risk profile. The rationale for conducting this phase 3 trial is to confirm the efficacy of C21 in subjects with COVID-19.

Objectives, Endpoints and Estimands:

Objectives	Endpoints
Primary	

Evaluate the efficacy of C21 versus placebo as add on to SoC on recovery in subjects with COVID-19.	
All-cause mortality up to Day 60.
Key secondary	
Time to sustained hospital discharge up to Day 60.Supplemental oxygen free days up to Day 29.Proportion of subjects free of respiratory failure, defined as an 8-point ordinal scale score ≤ 5, at Day 15.Proportion of subjects discharged from hospital and free of supplemental oxygen at Day 15.
Secondary	

 Evaluate the safety profile of C21 versus placebo as add on to SoC in subjects with COVID-19. 	
 Adverse events (AE)s. Serious AEs (SAE)s. Changes in safety laboratory assessments. Withdrawals due to AEs.

 Characterize the PK profile of C21 in subjects with COVID-19. 	
 PK parameters.

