4.3. Justification for Dose

Subjects will be treated with oral 100 mg C21 or placebo b.i.d. for 14 days.

The results of the completed phase 2 trial in COVID-19 subjects (VP-C21-006) and of the phase 1 trial in healthy subjects (VP-C21-003) indicate an acceptable safety and tolerability profile for the 100 mg b.i.d. dose. The risks of C21 in adults are considered primarily related to reversible alopecia seen at the higher dose of 200 mg b.i.d. In the phase 2 trial in COVID-19 subjects (VP-C21-006) and the phase 1 trial (VP-C21-003), the 100 mg b.i.d. dose did not cause any hair loss (Further details can be found in the IB). Alopecia is therefore not considered to present any significant safety risk to subjects in this trial.

In the phase 1 trial (VP-C21-003), 100 mg b.i.d. dosing prolonged the duration of the plasma concentration at therapeutic relevant levels. After oral administration, C21 was rapidly absorbed. On Day 8, median t_{max} was 0.33 hours after each dose post-dose, and C21 was measurable in plasma until 4-6 hours after the first and second dose. Lower doses than 100 mg b.i.d. may not provide maximal efficacy benefit.

In the completed phase 2 trial (VP-C21-006) in COVID-19 subjects, treatment with 100 mg b.i.d. for 7 days, reduced the need for extended oxygen supplementation.

The recently completed phase 2 trial (VP-C21-006) indicates that C21 can prevent hypoxic critical illness and based on the course of the disease, there is a strong rational to extend the treatment duration from 7 to 14 days. Furthermore, 27% of subjects within the C21 arm were still in need of oxygen (vs 45% on placebo) at the end of the 7 days treatment, highlighting an opportunity to treat for a longer period to gain additional benefit, with the aim of returning patients to normoxia.

There is not enough evidence to treat beyond 14 days at this stage.

Based on the above, C21 will be administered at an oral dose of 100 mg b.i.d. for 14 days in the present trial.

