9.5.5 Pharmacokinetics Analysis Set

The pharmacokinetics analysis set (PKS) is defined as subjects who were randomized to C21, exposed to IMP and with at least one post-IMP blood sample with quantifiable C21 concentration collected. Participants may be excluded from the PK analysis population if they have important protocol deviations that are judged to significantly impact the PK analyses. PK sample is limited among a pre-selected number of trial sites in a subgroup of approximately 10 subjects including those randomized to Placebo. Only samples from subjects randomized to C21 will be analyzed and included.

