12.7 Pharmacokinetics Analyses

All C21 plasma concentration data collected in this trial may be included in population PK and population PK/PD analyses with the objective of exploring the impact of covariates (e.g., body weight and age) on the PK of C21, or the relationship between the C21 exposure and selected efficacy and safety endpoints. If the PK population is not sufficient for analysis data will be listed only.

Blood PK samples will be collected before the first IMP administration (pre-dose) and 30 minutes, 1, 2, 3, 4, and 6 hours after the first IMP administration. Any population PK and population PK/PD analyses will be reported separately. Due to the unblinding nature of the data, PK analyses will be conducted after unblinding of the trial.

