12.7.2 Pharmacokinetic Parameters

The plasma C21 concentration data will be analyzed by non-compartmental methods with WinNonlin® (WNL) version 8.1 or higher unless stated otherwise and the following parameters will be derived and summarized:

- C_{max} – Observed maximum plasma concentration of C21, expressed in concentration units.
- t_{max} – Time to reach C_{max} following first dose of IMP, expressed in time units. If C_{max} occurs at more than one time point t_{max} will be assigned to the first occurrence of C_{max} .
- $AUC_{(0-6)}$ – Area under the plasma concentration curve from time zero to 6 hours. The below conditions will be followed:
 - Actual time will be used for calculating $AUC_{(0-6)}$
 - If the 6 hour sample was not taken then $AUC_{(0-6)}$ will not be calculated
 - $AUC_{(0-6)}$ will be calculated by WNL using extrapolation to actual time when there is a valid λ_z and the 24 hour sample is BQL and the concentrations thereafter are also BQL.
- $AUC_{(0-\infty)}$ – Area under the plasma concentration-time curve from time zero extrapolated to infinity. Adjusted r^2 for $t_{1/2}$ greater than 0.8 and $AUC\%Extrap \leq 20\%$ are required to obtain a reliable estimation of $AUC_{(0-\infty)}$. $AUC_{(0-\infty)}$ will be included in analysis/summaries only if these two criteria are met.
- AUC_{last} – Area under the plasma concentration curve from time zero to the last quantifiable concentration.
- $t_{1/2}$ – Apparent terminal half-life, expressed in time units. Adjusted r^2 greater than 0.8 is required to obtain a reliable $t_{1/2}$. $t_{1/2}$ will be included in analysis/summaries only if this regression criteria is met (all values will be listed).
- C_6 – Actual plasma concentration of C21 at 6 hours after IMP administration (C_6 will be analyzed using SAS® version 9.4 or higher)

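### The first post-dose PK sample (30 min) falls after the protocol's own phase 1 median tmax (0.33 h), so if patients absorb similarly, early peaks are missed and Cmax is understated

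*Protocol*

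**What the plan says.** A stated secondary objective is: "Characterize the PK profile of C21 in subjects with COVID-19" (Protocol Synopsis, repeated in Section 3). Protocol 8.6 and SAP 12.7.2 derive Cmax, tmax, AUC(0-6), AUClast, AUC to infinity, half-life and the 6 h concentration by non-compartmental analysis.

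The schedule is the same in both documents. Protocol 8.6 says "blood samples will be collected before the first IMP administration and 30 minutes, 1, 2, 3, 4 and 6 hours after the IMP administration"; SAP 12.7 has a pre-dose sample and then "30 minutes, 1, 2, 3, 4, and 6 hours after the first IMP administration". SAP 12.7.2 defines tmax as the time to reach Cmax "following first dose of IMP, expressed in time units", and Cmax is the observed maximum.

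Protocol 4.3 describes C21 as quickly absorbed and says that on Day 8 the median tmax "was 0.33 hours after each dose post-dose, and C21 was measurable in plasma until 4-6 hours after the first and second dose". The source is VP-C21-003, which the same section introduces through the results "of the phase 1 trial in healthy subjects (VP-C21-003").

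On numbers, SAP 9.5.5 says: "PK sample is limited among a pre-selected number of trial sites in a subgroup of approximately 10 subjects including those randomized to Placebo". Neither document explains why sampling starts at 30 min.

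**The concern.** Under these definitions tmax can only fall on a sampling time. A subject who peaks before the first post-dose draw is recorded with a tmax of about 0.5 h, and that subject's Cmax is a value from the declining part of the curve. A recorded tmax of 0.5 h then fits two different situations: absorption unchanged from phase 1, or somewhat slower absorption in patients. Separating these is part of what a PK profile in patients should show.

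The AUC rule may add to this. SAP 12.7.2 sets leading values below quantification to zero and uses the linear trapezoid up to tmax. The first half hour therefore becomes a straight line from zero to the 30 min value, which can cut off an early peak.

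What is at stake is a descriptive secondary objective in a small subgroup, plus the early absorption information available to any later population PK or PK/PD work. It does not reach the primary or key secondary efficacy analyses.

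**Working it through.** **Timing.** The 0.33 h figure is an observed phase 1 result. It cannot be reproduced, because the documents give no concentrations, half-life or tmax range. Converted: 0.33 x 60 = 19.8 min. The first draw is at 30 min, 10.2 min later. By the definition of a median, at least half of subjects would peak at or before 0.33 h if phase 1 carries over. With a lognormal spread around 0.333 h, P(tmax < 0.5) = Φ[ln(0.5/0.333)/s], where s = √ln(1 + CV²). An assumed CV of 20% gives 0.98 and a CV of 100% gives 0.69.

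**Model for the size (assumed, illustration only).** One compartment with absorption lag L:

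C(t) = A·[ka/(ka − ke)]·[exp(−ke(t − L)) − exp(−ka(t − L))], with ke = ln 2 / half-life.

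ka is solved from ln(ka/ke)/(ka − ke) = 0.333 − L, so that the true tmax is 0.333 h. Sample at 0, 0.5, 1, 2, 3, 4 and 6 h, apply the SAP's linear-up/log-down rule, and compare with the exact AUC(0-6).

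**One case in full: half-life 1 h, no lag.** ke = 0.693 and ka = 8.05. In units of A, C(0.333) = 0.794 and C(0.5) = 0.754, so observed/true Cmax = 0.754/0.794 = 0.95. The first trapezoid is 0.5 x 0.5 x 0.754 = 0.189, against an exact area of 0.329. Over 0-6 h the rule gives 1.276 against an exact 1.418, a ratio of 0.90.

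**Range.** Ratios are observed/true. Recorded tmax was 0.5 h in every planned-grid case.

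| Half-life (h) | Lag (h) | Cmax, planned | AUC(0-6), planned | AUC(0-6) with a 20 min draw |
|---|---|---|---|---|
| 0.5 | 0 | 0.93 | 0.84 | 0.92 |
| 0.5 | 0.25 | 0.82 | 0.98 | 1.12 |
| 1 | 0 | 0.95 | 0.90 | 0.95 |
| 1 | 0.25 | 0.90 | 1.00 | 1.07 |
| 2 | 0 | 0.97 | 0.94 | 0.97 |
| 2 | 0.25 | 0.95 | 1.00 | 1.04 |

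Cmax is 3-7% low with no lag and 5-18% low with a 0.25 h lag. AUC(0-6) runs from 16% low to no bias. A wider set of 36 assumed curves, including two-compartment shapes and a half-life of 0.25 h, gave Cmax 3.0-31.1% low in every case and AUC(0-6) from 21.1% low to 0.2% high.

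With a draw at 20 min, observed Cmax equals the true value by construction, because a sample sits on the assumed peak. In this model AUC is the same whether that draw replaces the 3 h sample or is added to it, since the log rule is almost exact on the late decline.

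**The case against.** The strongest reply is that 0.33 h need not apply here. It comes from healthy subjects at Day 8, whereas this trial samples hospitalised patients at first dose, and Protocol 6.2 allows a dispersion by mouth or feeding tube. The phase 1 value also depends on that study's own sampling times, which are not given. This stands. A reader might infer that the trial cannot measure tmax at all; the documents do not support that, because a peak at or after 0.5 h can be registered. Actual draw times are used, so a slightly early draw could also record a tmax a little under 0.5 h.

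A reader might also infer that AUC is necessarily biased low. That does not follow from the sampling times alone. A lag is plausible for a capsule, and with a lag of 0.25 h the planned grid is within about 2% of the true AUC(0-6), while a grid with a 20 min draw overshoots by 4-12%. Lag does not rescue Cmax, though: it makes the Cmax shortfall larger.

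Finally, the consequences are limited. Parameters are summarised descriptively, SAP 12.7 allows listing only if the data are insufficient, and no comparison with phase 1 is planned. Population PK works from concentrations and actual times, so the trapezoid error does not carry into it; it lacks only early absorption data. All of this bears on how much the point matters. None of it removes the gap before 30 min.

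**Conclusion.** The point holds as a minor, inexpensive improvement. The schedule starts after the only tmax the protocol reports, and nothing in either document compensates. If phase 1 absorption carries over to patients on Day 1, at least half of the C21 subjects peak before the first post-dose draw; their tmax is set by that draw and their Cmax is understated.

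The tmax and Cmax part rests on one condition, that patients absorb about as fast as the phase 1 subjects. The percentages rest on an assumed half-life, lag and model shape. Understatement of AUC(0-6) is possible, not established. With about 10 subjects including placebo, about 5 would be on C21 if the 1:1 ratio holds in the subgroup, and more subjects on the same grid would not remove the problem.

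**What to change.** **Subjects not yet sampled:** take a draw at about 20 min, in one of two ways.

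- Replace the 3 h draw. The number of draws and the blood volume do not change. The cost is fewer points for half-life and AUC to infinity. C21 was measurable only until 4-6 h, and SAP 12.7.2 treats later values below quantification as missing. If the 6 h value is lost, a subject peaking at 1 h keeps only the 2 h and 4 h points after the peak, which is too few for the adjusted r² criterion in SAP 12.7.2.
- Add the draw and keep 3 h. This protects the late decline. Seven draws of about 3 mL (21 mL) become eight (24 mL) in roughly 10 subjects; check the total against the 130 mL ceiling in Protocol Section 8.

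Either way, Protocol 8.6, SAP 12.7 and 12.7.1 and the sampling instructions change by a line each. Profiles from the two grids should be identified in the summaries. The change is for tmax and Cmax; it should not be presented as a sure gain for AUC.

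**Profiles already collected on the planned grid:** when the first post-dose sample is the highest, report tmax as at or before that sampling time, label that Cmax a lower bound, and do not compare either with phase 1. This costs a footnote and a reporting rule in SAP 12.7.2.

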8.7. Genetics

Genetics are not evaluated in this trial.

8.8. Biomarkers

- Plasma samples will be collected to investigate a range of laboratory parameters as potential biomarkers of inflammation, fibrosis, and viral activity including serology.

Samples will be collected according to the schedule described in the SoA and as detailed in laboratory manual provided separately to sites.

- Sponsor may store and analyze samples for up to 2 years after the end of the trial to achieve trial objectives.
- Biomarker results will be reported separately from the clinical trial report.

8.9. Immunogenicity Assessments

Immunogenicity is not evaluated in this trial.

8.10. Health Economics OR Medical Resource Utilization and Health Economics

Medical resource utilization and health economics parameters will be evaluated in terms of days hospitalized and days at intensive care unit. Additional analyses may be conducted outside of the clinical trial report.

9. Statistical Considerations

The statistical analysis plan will be finalized prior to unblinding, and it will include a more technical and detailed description of the statistical analyses described in this section. This section is a summary of the planned statistical analyses of the most important endpoints including primary and key secondary endpoints.

9.1. Statistical Hypotheses

The aim of this trial is to show superiority of C21 over placebo regarding selected efficacy measures. The null hypothesis to be tested for each endpoint will be that there is no difference between C21 and placebo, against the alternative hypothesis that C21 is better than placebo. All tests will be done using 2-sided alternatives.

9.1.1. Multiplicity Adjustment

The statistical comparisons for the primary efficacy endpoint and the key secondary endpoint will be carried out in following hierarchical order; all-cause mortality up to Day 60, time to sustained hospital discharge up to Day 60, supplemental oxygen free days up to Day 29, proportion of subjects free of respiratory failure at Day 15, and proportion of subjects discharged from hospital and free of supplemental oxygen at Day 15. This means that statistically significant results for the comparison in the higher rank are required to initiate the testing of the next comparison in the lower rank. Since a step-down procedure is used, each comparison will be tested at a significance level of 0.05 and an overall alpha level of 0.05 will be preserved.

9.2. Analysis Sets

For the purposes of analysis, the following analysis sets are defined:

Subject Analysis Set	Description
Intention to treat (ITT) analysis set	All randomized subjects. Subjects will be included in the analyses according to the intervention they were randomized to.
Per protocol (PP) analysis set	All subjects in the ITT set without major protocol deviations deemed to have an impact on efficacy readouts. In addition, subjects who prematurely discontinued IMP during the treatment period but continued with data collection in the trial will also be excluded from the PP. Subjects withdrawn from the trial unrelated to trial participation due to extraordinary circumstances (for example subjects lost-to follow up due to unstable geopolitical situation) may also be excluded from the PP set (further specified in the SAP). Subjects will be included in the analyses according to the intervention they were randomized to.
Safety analysis set	All randomized subjects who are exposed to IMP. Subjects will be analyzed according to the actual intervention received.

Subject Analysis Set	Description
PK analysis set	All subjects randomized to C21, exposed to IMP and with at least one post-IMP blood sample with quantifiable C21 concentration collected. Participants may be excluded from the PK analysis population if they have important protocol deviations that are judged to significantly impact the PK analyses.

